**Aim 2 – Test clinical, neurocognitive and functional impact of AMPH on TCT, and its relationship to target engagement:** We will determine if AMPH+TCT produces greater, faster or more durable clinical, neurocognitive or functional gains from baseline, compared to PBO+TCT, over a 30-session course of TCT. A Cohen’s  $d \geq 0.5$  for the main effect of drug (PBO vs. AMPH) or drug x session (#10, 20, 30) interaction in an LME model is the primary “Go” criteria. The main effect of drug assesses “greater” gains. Reverse Helmert contrasts for session assesses “faster” gains. A separate model comparing differences in outcomes at 12-weeks post-TCT assesses “more durable” gains. Secondary regression analyses will examine whether change in AMPH-enhanced APS learning (“within-subject” target engagement; Aim 1) predicts gains in Aim 2 outcome measures.

**Aim 3 – Biomarkers of AMPH-induced gains:** We will determine if baseline levels of specific neurocognitive or EEG-based measures, or changes in specific measures with initial AMPH exposure (Test 2 vs. 1), predict greater sensitivity to AMPH-enhanced neurocognitive, clinical or functional gains over 30-h of TCT. Regression analyses will assess whether specific candidate biomarkers predict AMPH-enhanced gains in outcome measures.

**Subject “throughput”:** We will enroll and screen 23 subjects/yr, test target engagement in 18 subjects/yr, and (conservatively) complete TCT training in 12 subjects/yr. This will yield 2 “target engagement” Aim 1 arms of  $n=27$ , and (conservatively) 2 TCT completion Aim 2 arms of  $n=18$ . Training capacity (2 TCT stations with morning and afternoon sessions on M, W and F, with T and Th “make-up” days for missed appointments, 48 weeks/year) allows for a “maximum throughput” of 19.2 subjects/yr. To reach the target of **12 TCT-completing subjects /year**, we would need to maintain training rates of **62.5% capacity**. This is well within our historical testing levels.

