Comparable analytic approaches will be used for neurocognition (MCCBc) and function (WHODAS) as described in "Research Strategy". Data will be described as means with SEM. Tests for normalcy will be applied to all data and non-parametric comparisons will be used if normalcy is not demonstrated. The Analysis Set for these data will be all subjects who have completed 30h of TCT and post-TCT clinical, neurocognitive and function assessments. When appropriate, missing data are handled via multiple imputation or full information maximum likelihood estimation.

Secondary regression analyses assess the predictive value of putative biomarkers on clinical, neurocognitive or functional gains from the addition of AMPH to TCT. Future studies with larger samples will assess potentially more informative models, e.g. Path Analysis to study moderating effects of APS AMPH sensitivity and biomarkers on both indirect (moderated-mediation) and direct paths between treatment and outcome.

Power analyses

Consistent with the FOA, this study will adequately power tests of target engagement (Aim 1) for traditional significance, while the "Go" signal for therapeutic impact (Aim 2) is based on effect size ($d=0.5$). To detect target engagement with $d=0.5$, 80% power, $\alpha=0.05$, test-retest correlation =0.8, and a linear treatment effect, $n=27$ randomized participants are required per group. This is a very conservative estimate of d for target engagement, since empirically, d for target engagement with 5 mg amphetamine was 0.85 (Fig. 3A). A future Confirmatory Efficacy trial will be powered to apply more robust approaches to Aim 2, e.g. Path Analysis¹⁰⁸ to study moderating effects of APS AMPH sensitivity and biomarkers on both indirect (moderated-mediation) and direct paths between treatment and outcome.

Project Modification: Statistical Analysis Plan

The original study design included separate, parallel assessments of amphetamine (AMPH) (vs. placebo (PBO)) and memantine (MEM) (vs. PBO) effects on TCT-associated clinical, neurocognitive and functional gains. However, these designs pre-dated the pandemic, and between the date that they were proposed (10/2019) and the project start date (8/2020), our institution implemented a pandemic-related shut-down of clinical research activities. Even with the gradual resumption of research activities, recruitment lagged significantly behind target levels. As a result, we made several pragmatic adjustments to the original study designs:

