1) Two separate but parallel protocols were approved by the UCSD IRB (protocols #191811, #201502) and posted on ClinicalTrials.gov. Due to the low recruitment numbers, the two parallel studies were combined and placebo groups were pooled, to yield a 3-group design 2) subject randomization changed from 1:1 to a 2:1 active : placebo ratio; and 3) adjustments were made to the planned statistical analyses, appropriate to the reduced sample size.

Based on known benefits of TCT in psychosis patients, no “placebo TCT” condition (e.g., video game) was included, for ethical and pragmatic reasons. Since all subjects received TCT, clinical gains over time in all groups might reflect, to some degree, the benefits of TCT. Pharmacologic augmentation by AMPH would only be evident if/when benefits in “TCT+active drug” groups exceeded those in “TCT+PBO” groups.

The primary goal of this study was to assess the clinical, neurocognitive and functional gains associated with the addition of AMPH to a full course of TCT. In total, there were 3 primary outcome measures and 5 secondary outcome measures. The primary clinical outcome measure was the Positive and Negative Symptom Scale (PANSS) total score; positive and negative subscale scores were secondary outcomes. Because they were highly correlated with total scores ($r=0.92$ at T_1), PANSS general scores are reported but are not outcomes. The primary neurocognitive outcome was the MCCB Composite Score. The primary functional outcome was the World Health Organization Disability Assessment Schedule (WHODAS 2.0, 12-item). Secondary clinical outcome measures also included the Patient Health Questionnaire (PHQ-9), the Young Mania Rating Scale (YMRS) and the Psychotic Symptoms Rating Scale (PSYRATS) hallucinations subscale.

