Clinical, neurocognitive and functional outcome scores were treated as continuous variables and analyzed in three ways. First, they were submitted to linear mixed-effects (LME) models⁵⁹ for both between-group (interaction model: TCT+AMPH vs. TCT+PBO) and within-group (time model: baseline vs. P30, all groups) analyses. LME analyses included data from all randomized subjects (including those who did not complete 30 AT sessions) and modeled random intercepts to account for within-subject dependencies. Second, because sample sizes fell well below target levels, to test the hypothesis that active drugs would augment the impact of a 30-session course of TCT, the effect size (Cohen's d) of the change from baseline to P30 (“difference score”) was calculated for both between-group (TCT+AMPH vs. AT+PBO) and within-group (baseline vs. P30, all groups) comparisons. Between-group effect sizes were calculated as:

$$d = [(drug score T_1 - drug score P30) - (PBO score T_1 - PBO score P30)] / SD_{wav}$$

where SD_{wav} is the weighted average standard deviation. Within-group effect sizes were calculated as:

$$d = (score at T_1 - score at P30) / SD_{av}$$

where SD_{av} is the average of the standard deviations of the T_1 and P30 measures^{60,61}.

Third, to disentangle the salutary contributions of TCT alone vs. TCT+active drug to within-subject effect sizes, a “threshold” for positive active drug effects was set at “*d=0.4 above PBO values*”:

$$d(\text{active drug}) \geq d(\text{PBO}) + 0.4.$$

Because clinical gains from TCT+PBO were expected to be approximately $d=0.4$, this added threshold of “ $d=0.4$ above PBO” for drug-enhanced TCT meant that an estimated combined large effect size (at least $d=0.8$) would be required for a drug effect to be viewed as meaningful. Outcomes using thresholds from $d=0.2$ to $d=0.6$ were reported.

The use of effect size comparisons in addition to p-values is common in clinical trials research as a way to measure effects independent of sample size. It is particularly useful when, as in the current study, sample sizes fall below targets identified based on traditional power analyses. Effect size “thresholds” have been used by others to argue that TCT neurocognitive benefits exceed levels produced via PBO or practice effects (generally $d \approx 0.18$).

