Indirect indicators of clinical impact included subject attrition, C-SSRS responses, treatment satisfaction and adverse events (AEs). AMPH group subjects were evaluated for abnormal involuntary movements (AIMS) and for deleterious effects of AMPH cessation (AMPH Cessation Symptom Assessment). Analyses included non-parametric (Chi-Square) and parametric (rmANOVA) tests.

Linear mixed-effects models for outcome measures included all subjects who were randomized; df were estimated using the Satterthwaite approximation. Between- and within-group effect sizes for clinical, neurocognitive and functional measures were calculated based on all subjects who completed 30 TCT visits and P30 testing (“completers”). For all analyses, α was set at 0.05; for analyses of the 5 secondary outcome measures, findings were also evaluated with a more restrictive alpha level (0.01) to correct for multiple comparisons.

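### Every effect size in the modified SAP is calculated in 30-session completers, with no stated link to the mixed-model d that decides Go for Aim 2

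*SAP*

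**What the plan says.** **Original plan.** The protocol (General Clinical Monitoring; Data Analysis) keeps non-completers in an intent-to-treat mixed model, uses full-information likelihood, and includes every case. The SAP repeats this in the paragraph after its secondary endpoints. For Aim 2, a d of at least 0.5 for the drug main effect or the drug by session (10, 20, 30) "interaction in an LME model is the primary" Go criterion (Protocol, Data Analysis, Aim 2), with d estimated by the EMAtools package.

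Under Go/No-Go decision and primary and secondary endpoints, however, the SAP states: "The Analysis Set for these data will be all subjects who have completed 30h of TCT and post-TCT clinical, neurocognitive and function assessments". The next sentence reads: "When appropriate, missing data are handled via multiple imputation or full information maximum likelihood estimation".

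**Project Modification (SAP).** The goal is the gain "associated with the addition of AMPH to a full course of TCT". The first analysis is a mixed model, and "LME analyses included data from all randomized subjects (including those who did not complete 30 AT sessions") are in it. The second is Cohen's d for change from baseline to the post-session-30 assessment (P30), introduced "to test the hypothesis that active drugs would augment the impact of a 30-session course of TCT". The third is a threshold: within-group d on active drug must be at least d on placebo plus 0.4. The combined large effect that this implies "would be required for a drug effect to be viewed as meaningful". Results for thresholds from 0.2 to 0.6 are also reported. The closing paragraph assigns populations: the mixed models use all randomized patients, and the effect sizes are "calculated based on all subjects who completed 30 TCT visits and P30 testing".

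**The concern.** There are two separate problems.

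First, the original text contradicts itself. An all-cases intent-to-treat model and a completer analysis set cannot both define the Aim 2 population. The missing-data sentence that follows the completer set mainly serves patients whom that set has just removed.

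Second, the modification settles the population for the p-values but not for the effect sizes. Aim 2 is decided on effect size, not significance, so this matters. The only d values that the modification defines are raw baseline-to-P30 differences in a group selected after randomization. No effect size is defined from the all-randomized model. The modification does not mention the 0.5 Go rule, and it does not say whether the completer d replaces that rule or supplements it.

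Whether a patient completes 30 sessions could depend on tolerability or on symptom change, and so on arm. If leaving is related to outcome differently in the two arms, completer arms are no longer comparable, even when the same number leaves each arm. The decision on a confirmatory trial could then rest on a selected subset.

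**Working it through.** **The plan's own figure.** The only sample size stated is for Aim 1: 27 per group for d = 0.5, 80% power, two-sided 0.05, test-retest r = 0.8. With change-score SD √(2(1 − 0.8)) = 0.632, n = 2 × (1.960 + 0.842)² × (0.632/0.5)² = 25.1, so 26 by normal approximation. The exact t calculation gives 27 (power 81.3%). The figure reproduces, but it does not power the Aim 2 d.

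**Inputs**
- From the documents: 27 randomized and 18 completing per arm, so loss = 18/54 = one third (Protocol, Recruitment and Retention Plan); r = 0.8 (stated for target engagement, borrowed here).
- Assumed: no drug effect; equal correlations across visits; loss random on placebo; in the AMPH arm, the propensity to leave correlates s = 0.3 to 0.5 with poor change.

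**Approximate bias of the completer d.** Removing the lowest third on a standard normal propensity raises the mean propensity of those who stay by φ(−0.431)/(2/3) = 0.3636/0.6667 = 0.545.
- (b) Leaving depends on the unobserved P30 change: bias ≈ s × 0.545 × 0.632 = 0.10 (s = 0.3) to 0.17 (s = 0.5).
- (a) Leaving depends on the observed session-10 change: with equal correlations, session-10 and P30 changes correlate 0.5, so the bias is half of that, 0.05 to 0.09.

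**Approximate chance of reaching +0.4.** SE = 0.632 × √(2/18) = 0.211. With no bias, P = 1 − Φ(0.4/0.211) = 2.9%. With bias 0.172, P = 1 − Φ(0.228/0.211) = 14%.

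**Simulation** (10,000 trials per row; completer figure = within-group d on AMPH minus that on placebo; mixed-model figure = P30 contrast from an all-randomized random-intercept model with baseline, session 10, 20 and P30 scores, divided by the pooled baseline SD):

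| Leaving in the AMPH arm | Completer bias | Completer P(≥0.4) | Mixed-model bias | Mixed-model P(≥0.4) |
|---|---|---|---|---|
| Unrelated to outcome | 0.00 | 3.7% | 0.00 | 2.7% |
| (a) s = 0.3 | 0.054 | 5.9% | 0.00 | 2.6% |
| (a) s = 0.5 | 0.092 | 8.3% | 0.00 | 2.7% |
| (b) s = 0.3 | 0.109 | 9.3% | 0.073 | 5.1% |
| (b) s = 0.5 | 0.181 | 15.3% | 0.120 | 8.0% |
| (b) s = 0.5 in both arms | 0.00 | 3.1% | 0.00 | 1.8% |

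The simulated values agree with the approximations; dividing by sample SDs in small groups makes them slightly larger. In (b) the mixed model removes about a third of the bias: 1 − 0.120/0.181 = 34%.

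**The visits matter.** The modification does not list the visits in its interaction model. With baseline and P30 only, the mixed-model bias is 0.041 to 0.072 in (a) and 0.095 to 0.158 in (b). That is 76–78% and 87% of the completer bias.

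**Sensitivity.** At r = 0.6, the completer bias is 0.073 to 0.126 in (a) and 0.149 to 0.255 in (b). P(≥0.4) is 14–19% and 20–32%, against about 9% with no selection. With selection of 0.5 on placebo only (r = 0.8), the bias is −0.09 to −0.18.

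Two limits apply. The simulated mixed-model d is a P30 contrast, not the EMAtools d of the Go rule, so the 0.4 column compares size only. The between-group d with the weighted SD was not simulated separately.

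**The case against.** The plan has real safeguards. The modification lists the all-randomized mixed model first and describes effect sizes as an addition to p-values. It reports thresholds from 0.2 to 0.6, a range wider than the bias found at r = 0.8. Attrition is expected to be roughly balanced and is compared by arm. The SAP's section on unexpected results anticipates non-random drop-out and would add auxiliary variables to the mixed model. The completer d has a stated purpose, the effect of a full course. The imputation sentence could still serve completers who miss session 10 or 20. The completer-set sentence follows one on MCCB and WHODAS, so its reach to PANSS is a natural reading but not explicit.

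All of this stands, and it limits the point. None of it corrects a raw completer d: auxiliary variables act only inside the mixed model, drop-out counts show unequal loss but not unequal selection, and interest in a full course does not make completer arms comparable. Even on the narrow reading, two of the three primary outcomes are affected.

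A reader might infer more than the documents support:
- **That the modified analysis as a whole is completers-only.** It is not; the mixed model uses all randomized patients.
- **That the completer d has replaced the Go d.** The text does not say so. The gap is that it says neither.
- **That 2:1 allocation makes the AMPH arm twice the placebo arm, so the problem is larger.** Two studies were combined and their placebo groups pooled. The AMPH to pooled-placebo ratio is not given and may be about 1:1.
- **That large chances of passing 0.4 in small samples reflect selection.** Part is small-sample noise, as the 9% no-selection figure at r = 0.6 shows.

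**Conclusion.** The concern holds as a conflict over analysis population and an unstated decision rule. The completer analysis set contradicts the plan's all-cases model. The modification restores all randomized patients for the mixed model only, leaves every d and the +0.4 rule in completers, and does not connect them to the 0.5 Go rule.

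The size is moderate. Under the main assumptions (r = 0.8, selection in the AMPH arm only) the completer d is biased by about 0.05 to 0.09 when leaving follows observed change, where the full mixed model is about unbiased. When leaving follows unobserved change, the bias is 0.11 to 0.18, against 0.07 to 0.12 for the mixed model. The chance of passing +0.4 rises from about 4% to 6–15% per outcome.

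The selection strength, its restriction to one arm and the correlation are assumptions; the modified arm sizes and actual attrition are not given. The bias may favour either arm, is zero with equal loss and equal selection, and by itself does not reach 0.4 or 0.5. It would therefore be wrong to conclude that selection alone could produce a passing result. This should be fixed, but it does not invalidate the trial.

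**What to change.** 1. Delete the completer analysis-set sentence in the SAP's Go/No-Go section, or relabel it as a supportive analysis, so that it agrees with the all-cases rule.
2. For each primary outcome, report the effect size with a 95% confidence interval from the all-randomized mixed model using baseline, session 10, session 20 and P30 scores. Base the Go decision on the d already defined: drug main effect or drug by session, from EMAtools, at 0.5. If a P30 contrast divided by the pooled baseline SD is also reported, say that it is a different d, and do not apply the 0.5 or 0.4 cut-off to it as if that had been planned.
3. Label the completer d and the +0.4 rule, with its 0.2 to 0.6 range, as supportive answers to the full-course question.
4. Optionally, add a sensitivity analysis that shifts leavers' imputed P30 scores separately by arm.

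The modification is written in the past tense. If the analyses are already run, report the mixed-model d beside the completer d and say whether the conclusion depends on which is used.

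The cost is SAP wording and a few lines of code on a model already specified, plus one extra analysis if item 4 is taken up. The reported d may be smaller.
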